## **6.7 PHARMACOKINETIC ANALYSES**

Plasma/serum concentrations of obinutuzumab, *rituximab*, polatuzumab vedotin, and lenalidomide will be tabulated, summarized, and plotted after appropriate grouping. As appropriate, PK parameters (e.g., area under the curve [AUC], time to maximum concentration [ $t_{max}$ ], maximum concentration [ $C_{max}$ ], half-life [ $t_{1/2}$ ]) may also be calculated, tabulated, and summarized after appropriate grouping. Additional PK and PK/PD analyses (e.g., population modelling including pooled analyses across studies) may also be performed as appropriate. If done, these additional analyses may be reported separately from the CSR. At the discretion of the Sponsor, all analyses may be extended to include relevant biotransformation products of polatuzumab vedotin or lenalidomide.

## **6.8 IMMUNOGENICITY ANALYSES**

The numbers and proportions of post-treatment HAHA- or HACA-, and ATA-positive patients and HAHA- or HACA-, and ATA-negative patients at baseline and during both the treatment and follow-up periods will be summarized by histologic subtype. Patients are considered to be ATA positive if they are ATA negative at baseline but develop an ATA response following study treatment administration (treatment-induced ATA response) or if they are ATA positive at baseline and the titer of one or more post-baseline samples is at least 4-fold greater (i.e.,  $\geq 0.60$  titer units) than the titer of the baseline sample (treatment-enhanced ATA response). Patients are considered to be ATA negative if they are ATA negative at baseline and all post-baseline samples are negative or if they are ATA positive at baseline but do not have any post-baseline samples with a titer that is at least 4-fold greater than the titer of the baseline sample (treatment unaffected).

The relationship between HAHA or HACA, and ATA status and safety, efficacy, PK, and biomarker endpoints will be explored as appropriate.

## **6.9 BIOMARKER ANALYSES**

Exploratory analyses of biomarkers related to tumor biology and study treatment MOA will be conducted. Analyses will assess the prognostic and/or predictive value of candidate biomarkers separately for each histologic subtype with respect to both IRC- and investigator-assessed outcomes. Specifically, the association between candidate biomarkers and PET-CT-defined CR rate and objective response (CR+PR) rate, and potentially other measures of efficacy and safety, will be explored to assess potential prognostic or predictive value. These analyses may not be included in the final study report because of their exploratory nature. In addition to analysis in the context of this study, data will also be explored in aggregate with data from other studies.

## **6.10 INTERIM ANALYSES**

It is anticipated that at least two interim analyses, one per histology, will be conducted during the expansion phase of the study, when at least 15 patients *in each histology* have been evaluated for PET-CT–defined CR at EOI. Additional analyses may be conducted to guide early stopping of enrollment for safety on the basis of observed toxicities and the ability to maintain chemotherapy dose intensity.

During the expansion phase, a *modified version of the predictive probability design (Lee and Lui 2008)* may be used to guide early stopping for futility by comparing the observed proportion of patients who achieve a PET-CT–defined CR at EOI in each indication-specific expansion cohort with that in historical controls. Updated estimates for the assumed historical control PET-CT–defined CR rate will be available from currently ongoing studies by the time of the first interim analysis. *The design is based on Lee and Lui 2008, with the modification that the uncertainty in the historical control data is fully taken into account by utilizing a beta posterior on the control response rate. Interim analysis decision rules will be based on the predicative probability that the trial will have a positive outcome if carried out to completion and will use the historical control data available at the time of analysis.*

If, at any time, an interim analysis suggests that the proportion of patients achieving a PET-CT–defined CR for one of the indication-specific expansion cohorts is lower than expected, the IMC will review the data and decide whether to recommend an early decision to stop enrollment in that subgroup.

Additional review of safety and/or efficacy data by the IMC may be requested by and carried out at the discretion of the Medical Monitor. Further details regarding the rules and guidelines of data review will be provided to the IMC in an IMC charter.

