### **1.3.2 Clinical Studies with Polatuzumab Vedotin**

To date, clinical data on polatuzumab vedotin are available from one completed Phase I/Ib study (DCS4968g) and the ongoing Phase Ib/II Studies GO27834, GO29044, GO29833, BO29561, and GO29365 in patients with B-cell lymphoma.

*DCS4968g evaluated polatuzumab vedotin as a single agent and in combination with rituximab in patients with R/R B-cell lymphoma.*

*GO27834 is evaluating polatuzumab vedotin in combination with either obinutuzumab or rituximab in patients with R/R FL or DLBCL.*

*GO29044 is evaluating polatuzumab vedotin in combination with rituximab plus cyclophosphamide, doxorubicin, and prednisone (R-CHP) or obinutuzumab plus cyclophosphamide, doxorubicin, and prednisone (G-CHP) in patients with newly diagnosed or R/R B-cell lymphoma.*

*GO29365 is evaluating polatuzumab vedotin in combination with bendamustine plus rituximab or obinutuzumab in patients with R/R FL or DLBCL.*

Available efficacy and safety results from these studies are summarized in Sections [1.3.2.1](#) and [1.3.2.2](#), respectively.

For more detailed clinical information on polatuzumab vedotin, including clinical pharmacology data, refer to the Polatuzumab Vedotin Investigator's Brochure.

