#### **1.3.2.1 Clinical Efficacy of Polatuzumab Vedotin in Patients with B-Cell Lymphoma**

Polatuzumab vedotin demonstrated clinical activity as a single agent.

In Study DCS4968g, at the 2.4-mg/kg dose, objective responses (CR or PR) were observed in 7 of 16 patients (44%) with R/R indolent B-cell lymphoma (FL, marginal zone lymphoma [MZL], or small lymphocytic lymphoma [SLL]) and 14 of 27 patients (52%) with R/R DLBCL. *At a dose of 1.8 mg/kg, a PR was observed in 2 of 4 patients with DLBCL and in 2 of 2 patients with MCL, and no objective responses were observed in the 5 patients with CLL. The median duration of response was 6.2 months (95% CI: 3.3, 19.3 months) for the 2.4-mg/kg dose and 6.6 months (95% CI: 2.3, 11.4 months) for the 1.8-mg/kg dose. At the 2.4-mg/kg dose, median PFS was 7.9 months (95% CI: 3.0, 11.6 months) for patients with indolent B-cell lymphoma and 5.0 months (95% CI: 2.3, 6.8 months) for patients with DLBCL. Median PFS was 4.6 months (95% CI: 1.4, 13.9 months) for patients with DLBCL treated at the 1.8-mg/kg dose.*

*Polatuzumab vedotin also demonstrated clinical activity when administered in combination with rituximab. In Study DCS4968g, at a dose of 2.4 mg/kg, objective responses were observed in 7 of 9 patients with indolent B-cell lymphoma, DLBCL, or MCL (78%); 2 of those 7 patients had CRs. Median duration of response among these patients was 12.3 months (95% CI: 4.3, not estimable [NE]). Median PFS was 12.5 months (95% CI: 6.9, 17.4 months).*

*Preliminary data show that for patients in Study GO27834 who received polatuzumab vedotin (2.4 mg/kg) in combination with rituximab overall responses were observed in 14 of 20 patients with R/R FL (70%; 9 patients with CRs) and 21 of 39 patients with R/R DLBCL (54%; 8 patients with CRs). For patients who received polatuzumab vedotin (1.8 mg/kg) in combination with rituximab, objective responses were observed in 15 of 20 patients with FL (75%; 6 patients with CRs).*

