## 6.1 DETERMINATION OF SAMPLE SIZE

Limited dose finding will be conducted during the dose-escalation phase of this study. The estimated sample size follows from the dose-escalation rules for a standard 3+3 algorithm, as outlined in Section 3.1. It is anticipated that enrollment of 5 cohorts of 3–6 patients each, for a total of 18–30 patients, will be required to establish the RP2D during the dose-escalation phase *for patients with R/R FL. An additional 3 possible cohorts of 3–6 patients each, for a total of 12–18 patients will be required to establish the RP2D during the dose-escalation phase for patients with R/R DLBCL.*

Approximately 80 patients (40 patients with FL and 40 patients with DLBCL) will be enrolled during the expansion phase. Overall, approximately 110–128 patients will be enrolled in the study.

The primary efficacy analysis will be the estimation of the true proportion of patients expected to obtain a PET-CT–defined CR at EOI.

Data from completed and ongoing studies in similar disease settings will be used as historical controls for comparison. Currently available data indicate that the historical CR rate based on PET-CT scans is 40% for R/R FL and DLBCL.

A sample size of 40 patients is deemed sufficient to provide adequate precision for the point estimate and for the lower bound of the two-sided 90% CI to rule out a clinically uninteresting probability of response of <55%, assuming an observed PET-CT–defined CR rate of 70%.

Table 22 lists the two-sided 90% Clopper-Pearson exact CIs for the true probability of achieving a PET-CT–defined CR at EOI for a range of observed proportions based on a sample of 40 patients.

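### Does the optional futility look in Section 6.10 need its success criterion and historical control fixed in the plan?

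*Combined protocol and SAP*

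**What the plan says.** Section 6.10 plans at least one interim analysis per histology in the expansion phase, when at least 15 patients have been evaluated for PET-CT-defined CR at end of induction. A modified predictive probability design may be used to guide stopping for futility. It compares the cohort with historical controls through a beta posterior on the control rate. The section states that "Interim analysis decision rules will be based on the predicative probability that the trial will have a positive outcome" and that the rules "will use the historical control data available at the time of analysis". Updated control estimates "will be available from currently ongoing studies by the time of the first interim analysis". If the CR rate looks lower than expected, the IMC reviews the data and decides whether to recommend closing that cohort. "Further details regarding the rules and guidelines of data review will be provided to the IMC in an IMC charter".

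Section 6.1 says that "the historical CR rate based on PET-CT scans is 40% for R/R FL and DLBCL", without a source or sample size. It separately justifies 40 patients per histology by the ability of the lower 90% confidence limit "to rule out a clinically uninteresting probability of response of <55" per cent if 70% is observed. Section 6.6.1 makes the primary analysis an estimate of the IRC-assessed CR proportion with an exact 90% interval. It contains no test.

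**The concern.** A predictive-probability rule cannot be computed without a success criterion, a control data set with its size, a prior and a cut-off. Section 6.10 gives none of these in full. The trial is open-label and, under Section 3.1.4, the IMC includes sponsor staff, so a control settled at the time of analysis could be settled after responses are visible.

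The protocol's own background shows how far the control might move. Section 1.3.2 lists "the ongoing Phase Ib/II Studies GO27834, GO29044, GO29833, BO29561, and GO29365 in patients with B-cell lymphoma". From one of these, Section 1.3.2.1 reports "21 of 39 patients with R/R DLBCL (54%; 8 patients with CRs", about half the 40% in Section 6.1. If low counts of this kind became the control, the look would seldom stop a weak DLBCL regimen. If 40% were used, it usually would. At stake is whether up to 25 further patients per histology are enrolled.

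**Working it through.** **Reproducing the plan's figure.** Section 6.10 gives no predictive probability to reproduce. The related figure is the 70% row of Table 22. The exact 90% limits for 28/40 are the 5% quantile of Beta(28, 13) and the 95% quantile of Beta(29, 12): 0.5597 and 0.8169. This matches the printed (0.56, 0.82), and 28/40 is the first count whose lower limit exceeds 0.55 (27/40 gives 0.5337).

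**Inputs from the documents.** Look at 15 and final n of 40 (Sections 6.10 and 6.1); 40% control (Section 6.1). R/R DLBCL CR counts in Section 1.3.2.1:

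- 8/39: rituximab, polatuzumab vedotin 2.4 mg/kg
- 0/15: obinutuzumab, 1.8 mg/kg
- 2/7: bendamustine and rituximab, 1.8 mg/kg
- 2/8: bendamustine and obinutuzumab, 1.8 mg/kg

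All four pooled: 8+0+2+2 = 12 of 39+15+7+8 = 69. Rituximab arms only: 8+2 = 10 of 39+7 = 46.

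**Assumed, because the plan does not give them.** Beta(1,1) priors; success at n = 40 if P(pE > pC) exceeds 0.90 or 0.95; stop if predictive probability is below 5% or 10%; effective historical n of 20, 50, 100, 200 or 500 for the 40% control.

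**Formulas.** With x CRs in 40, pE ~ Beta(1+x, 41−x). With r CRs in n controls, pC ~ Beta(1+r, 1+n−r). The bar b is the smallest x that passes the threshold. At 6/15, the predictive probability is P(Y ≥ b−6), where Y is beta-binomial with 25 trials and parameters 7 and 10.

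| Control | Bar of 40 | Predictive probability at 6/15 | Stop at or below, of 15 |
|---|---|---|---|
| 40%, n 20 to 500 | 21 to 26 | 0.8% to 13.9% | 5 to 7 |
| 2/7 | 23 to 26 | 0.8% to 5.5% | 5 to 7 |
| 10/46 | 14 to 16 | 57% to 76% | 2 to 3 |
| 12/69 | 12 to 13 | 84% to 90% | 1 to 2 |

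With Beta(0.5,0.5) priors the 12/69 row becomes 82% to 89%. If 40% is treated as a fixed constant, 6/15 gives 9% to 20%.

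**Chance of stopping, P(X ≤ k of 15).**

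- True rate 30%: k=1, 3.5%; k=2, 12.7%; k=3, 29.7%; k=5, 72.2%; k=7, 95.0%.
- True rate 70%: k=5, 0.4%; k=7, 5.0%; below 0.1% for k of 3 or less.

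**Does the control decide the advice at 6/15?** The 40% grid has 5 historical sizes × 2 thresholds × 2 cut-offs = 20 settings. A stop is signalled in 3 of 10 at the 5% cut-off and 7 of 10 at the 10% cut-off, so 10 of 20. In the other 10, enrollment continues, as it would with 12/69.

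**Is 12/69 a fair control?** Section 6.10 limits the comparison to PET-CT-defined CR, and for this trial's patients to end of induction. Section 1.3.2.1 states neither the imaging basis nor the timepoint for these counts. Of the 69 patients, 39 received the 2.4 mg/kg dose whose development Section 1.3.2.2 says has ended. Another 15+8 = 23 received obinutuzumab, which this protocol replaced with rituximab for DLBCL. Only 69−39−23 = 7 match on both antibody and dose, and their 2/7 gives results inside the range for 40%.

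**The case for a change.** The strongest case for a change is that the control is expressly left open until the analysis. A charter faithful to Section 6.10 could keep that freedom, and this is the only planned efficacy-based stop for each cohort. Writing the inputs down would take one paragraph. The sensitivity does not rest on the 12/69 pool alone: at a true CR rate of 30%, the 10/46 control stops 13% to 30% of the time, against 72% to 95% with a 40% control.

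That sensitivity stands, and so does the observation that the rule is not computable from Section 6.10 alone. The step to a needed change does not. That the control would be chosen after seeing responses is a possibility, not something the plan provides for. Freezing the control early also has a price, because the plan chose to use history as it matures in ongoing studies and to carry its uncertainty in a beta posterior. An early cut-off would give up some of that information for more certainty about the rule. How the 55% figure relates to the look is for the sponsor to say. Section 6.1 uses it to justify precision, and Section 6.10 compares with history.

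**Conclusion.** No change to the plan is needed. What is missing is operating detail for an optional look whose only output is a possible IMC recommendation. The IMC charter is the natural place for it, and since the charter was not supplied, its absence here does not show that the detail is lacking. An analyst setting up the rule would start from the one PET-CT control rate the plan states, 40%. Across the assumed settings this gives a stop at no more than 5 to 7 of 15, and a 0.4% to 5% chance of stopping a regimen with a true rate of 70%.

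The dependence on the control is real, but the widest contrast (84% to 90% against 1% to 14% at 6/15) requires a pooled control that the plan never names and that is not shown to meet its PET-CT definition. All these figures rest on assumed thresholds, cut-offs, priors and historical sizes. The primary CR estimate and its interval are computed the same way whatever futility rule is used.

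The rounding in Table 22 is a separate clerical matter. The rows for 22/40, 32/40 and 34/40 have limits cut off rather than rounded, and 0.72 is not a whole count of 40. The 28/40 row on which the sample-size statement relies is correct.

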## **7. DATA COLLECTION AND MANAGEMENT**

### **7.1 DATA QUALITY ASSURANCE**

The Sponsor will be responsible for data management of this study, including quality checking of the data. Data entered manually will be collected via EDC through use of eCRFs. Sites will be responsible for data entry into the EDC system. In the event of discrepant data, the Sponsor will request data clarification from the sites, which the sites will resolve electronically in the EDC system.

The Sponsor will produce an EDC Study Specification document that describes the quality checking to be performed on the data. Central laboratory data and any other externally-generated electronic study data will be sent directly to the Sponsor, using the Sponsor's standard procedures to handle and process the electronic transfer of these data.

eCRFs and correction documentation will be maintained in the EDC system's audit trail. System backups for data stored by the Sponsor and records retention for the study data will be consistent with the Sponsor's standard procedures.

## **7.2 ELECTRONIC CASE REPORT FORMS**

eCRFs are to be completed through use of a Sponsor-designated EDC system. Sites will receive training and have access to a manual for appropriate eCRF completion. eCRFs will be submitted electronically to the Sponsor and should be handled in accordance with instructions from the Sponsor.

All eCRFs should be completed by designated, trained site staff. eCRFs should be reviewed and electronically signed and dated by the investigator or a designee.

At the end of the study, the investigator will receive patient data for his or her site in a readable format on a compact disc that must be kept with the study records. Acknowledgement of receipt of the compact disc is required.

## **7.3 SOURCE DATA DOCUMENTATION**

Study monitors will perform ongoing source data verification to confirm that critical protocol data (i.e., source data) entered into the eCRFs by authorized site personnel are accurate, complete, and verifiable from source documents.

Source documents (paper or electronic) are those in which patient data are recorded and documented for the first time. They include, but are not limited to, hospital records, clinical and office charts, laboratory notes, memoranda, patient-reported outcomes, evaluation checklists, pharmacy dispensing records, recorded data from automated instruments, copies of transcriptions that are certified after verification as being accurate and complete, microfiche, photographic negatives, microfilm or magnetic media, X-rays, patient files, and records kept at pharmacies, laboratories, and medico-technical departments involved in a clinical trial.

Before study initiation, the types of source documents that are to be generated will be clearly defined in the Trial Monitoring Plan. This includes any protocol data to be entered directly into the eCRFs (i.e., no prior written or electronic record of the data) and considered source data.

Source documents that are required to verify the validity and completeness of data entered into the eCRFs must not be obliterated or destroyed and must be retained per the policy for retention of records described in Section 7.5.

To facilitate source data verification, the investigators and institutions must provide the Sponsor direct access to applicable source documents and reports for trial-related monitoring, Sponsor audits, and IRB/EC review. The study site must also allow inspection by applicable health authorities.

## **7.4 USE OF COMPUTERIZED SYSTEMS**

When clinical observations are entered directly into a study site's computerized medical record system (i.e., in lieu of original hardcopy records), the electronic record can serve as the source document if the system has been validated in accordance with health authority requirements pertaining to computerized systems used in clinical research. An acceptable computerized data collection system allows preservation of the original entry of data. If original data are modified, the system should maintain a viewable audit trail that shows the original data as well as the reason for the change, name of the person making the change, and date of the change.

## **7.5 RETENTION OF RECORDS**

Records and documents pertaining to the conduct of this study and the distribution of IMP, including eCRFs, Informed Consent Forms, laboratory test results, and medication inventory records, must be retained by the Principal Investigator for at least 15 years after completion or discontinuation of the study, or for the length of time required by relevant national or local health authorities, whichever is longer. After that period of time, the documents may be destroyed, subject to local regulations.

No records may be disposed of without the written approval of the Sponsor. Written notification should be provided to the Sponsor prior to transferring any records to another party or moving them to another location.

## **8. ETHICAL CONSIDERATIONS**

### **8.1 COMPLIANCE WITH LAWS AND REGULATIONS**

This study will be conducted in full conformance with the ICH E6 guideline for Good Clinical Practice and the principles of the Declaration of Helsinki, or the laws and regulations of the country in which the research is conducted, whichever affords the greater protection to the individual. The study will comply with the requirements of the ICH E2A guideline (Clinical Safety Data Management: Definitions and Standards for Expedited Reporting). Studies conducted in the United States or under a U.S. Investigational New Drug (IND) application will comply with U.S. FDA regulations and applicable local, state, and federal laws. Studies conducted in the European Union or European Economic Area will comply with the E.U. Clinical Trial Directive (2001/20/EC).

### **8.2 INFORMED CONSENT**

The Sponsor's sample Informed Consent Form will be provided to each site. If applicable, it will be provided in a certified translation of the local language. The Sponsor or its designee must review and approve any proposed deviations from the Sponsor's sample Informed Consent Forms or any alternate consent forms proposed by the site (collectively, the "Consent Forms") before IRB/EC submission. The final IRB/EC-approved Consent Forms must be provided to the Sponsor for health authority submission purposes according to local requirements.

If applicable, the Informed Consent Form will contain separate sections for any optional procedures. The investigator or authorized designee will explain to each patient the objectives, methods, and potential risks associated with each optional procedure. Patients will be told that they are free to refuse to participate and may withdraw their consent at any time for any reason. A separate, specific signature will be required to document a patient's agreement to participate in optional procedures. Patients who decline to participate will not provide a separate signature.

The Consent Forms must be signed and dated by the patient or the patient's legally authorized representative before his or her participation in the study. The case history or clinical records for each patient shall document the informed consent process and that written informed consent was obtained prior to participation in the study.

The Consent Forms should be revised whenever there are changes to study procedures or when new information becomes available that may affect the willingness of the patient to participate. The final revised IRB/EC-approved Consent Forms must be provided to the Sponsor for health authority submission purposes.

Patients must be re-consented to the most current version of the Consent Forms (or to a significant new information/findings addendum in accordance with applicable laws and IRB/EC policy) during their participation in the study. For any updated or revised Consent Forms, the case history or clinical records for each patient shall document the informed consent process and that written informed consent was obtained using the updated/revised Consent Forms for continued participation in the study.

A copy of each signed Consent Form must be provided to the patient or the patient's legally authorized representative. All signed and dated Consent Forms must remain in each patient's study file or in the site file and must be available for verification by study monitors at any time.

For sites in the United States, each Consent Form may also include patient authorization to allow use and disclosure of personal health information in compliance with the U.S. Health Insurance Portability and Accountability Act of 1996 (HIPAA). If the site utilizes a separate Authorization Form for patient authorization for use and disclosure of personal health information under the HIPAA regulations, the review, approval, and other processes outlined above apply except that IRB review and approval may not be required per study site policies.

